6. SUBJECT RECRUITMENT & SCREENING

Based on the results from Cotton et al, median transfusion in the component therapy group was 6 PRBC in the first 24 hours and 4 PRBC equivalents in the whole blood group. The standard deviation (estimated from the interquartile range) was approximately 4. Thus with an expectation of alpha = 0.05 and expected power of 90% to detect a similar 2 unit difference in transfusion volume, a sample size of 190 should be sufficient; thus our projected sample size of 200 should be more than adequate. Age range will be 18 years and older, and only males will be included in the study. Our expected racial/ethnic distribution will be approximately 60% white, 15% black, 8% Asian, and 18% other race. No actual recruitment will be performed; rather all qualifying patients will be included. Consent waiver is being requested.

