8. STUDY DESIGN

a. Background or rationale for this study.

Whole blood transfusion was used in World War I, World War II, Korea and Vietnam. By the end of the Vietnam conflict, whole blood had been separated into components for ease of use and more focused transfusion. As a result, transfusion practices did not catch up with the available units. More recent investigations have revealed that patients have fewer deaths from hemorrhage when the ratios of FFP:RBC units and platelet:RBC units approaches 1:1. Furthermore, the success of “walking blood banks” with fresh whole blood transfusion in the 2nd Iraq war and the war in Afghanistan have prompted new interest in the civilian use of whole blood. While civilian centers cannot use walking blood banks as we do not have a pre-screened population from which to draw, low-titer type O positive whole blood (LTOWB) can be used. One LTOWB unit is equivalent to one unit of PRBC and one unit of FFP. While LTOWB has been studied, the inclusion criteria for past studies has been less inclusive than in this trial, specifically excluding patients with severe traumatic brain injuries even if they also had exsanguinating hemorrhage. Furthermore, at Loma Linda University Medical Center we will have the opportunity to randomize patients to receive whole blood as their first transfusion, thus maximizing the potential benefits. Finally, we have the opportunity to study the coagulopathy associated with these patients by using viscoelastic testing.

b. Objectives

1. Evaluate PRBC equivalents transfused in each group in the first 24 hours (Primary outcome)
2. Evaluate total transfusion in each group in the first 24 hours (Secondary Outcome) including breakdown by FFP equivalents, platelet units, and cryoprecipitate
3. Evaluate 6 hour, 24 hour, and hospital mortality (Secondary Outcome)
4. Evaluate ICU outcomes in each group:
 1. ICU length of stay

- 2. Ventilator days
- 3. SOFA score on day of ICU discharge
- 4. Presence of ARDS?
- 5. Presence of TRALI?
- 6. Presence of DVT/PE?
- 7. Necessity for Dialysis?
- 8. Necessity for Tracheostomy?
- 5. Evaluate viscoelastic testing parameters in both groups when sent on arrival in ICU
 - 1. Percentage of patients with EXTEM clotting time > 80 sec
 - 2. Percentage of patients with EXTEM amplitude at 10 min < 40mm and FIBTEM amplitude at 10 min \leq 10mm
 - 3. Percentage of patients with EXTEM amplitude at 10 min < 40mm and FIBTEM amplitude at 10 min > 10mm

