 - 4. Percentage of patients with maximum thrombolysis > 15%
- 6. Interval analyses to be performed after 6 and 12 months with provision to continue the study out to 24 months.
 - 1. Stopping rule: A statistically significant difference in hospital mortality at 6 months or 12 months
 - 1. If in favor of LTOWB, consideration of trial termination and making LTOWB the primary standard of care for all trauma patients receiving emergency transfusion except for child-bearing age females (unless Rh immunoglobulin can be administered)
 - 2. If in favor of component therapy, consideration of trial termination and making component therapy the primary standard care for all trauma patients receiving emergency transfusion
- c. Procedures involved (Research Interventions)

*Chronological order of all research interventions, **distinguishing standard of care vs. research intervention.***

- 1. Level A trauma paged out with gender of patient
- 2. For female patients, care proceeds as normal
 - 1. Standard trauma cooler containing 4 units O- PRBC and 4 units FFP dispatched to trauma bay (if overall supply is short the first cooler may contain 2 units O- PRBC and 2 units FFP)
 - 2. Transfusion proceeds per trauma and ED team
 - 3. Patient data not included in the study

3. For male patients, the blood bank will randomize patients to the LTOWB group or the CT (component therapy) group based on a prespecified calendar-based randomization scheme by week:
 1. LTOWB: Cooler containing 2 or 4 units of LTOWB dispatched to trauma bay depending on supply
 2. CT: Standard trauma cooler containing 4 units O+ PRBC and 4 units FFP dispatched to trauma bay (if overall supply is short the first cooler may contain 2 units O+ PRBC and 2 units FFP)
 3. Transfusion proceeds per trauma and ED team
 4. Blood work (CBC, BMP, tox screen, ROTEM viscoelastic test, PT/INR, PTT, venous lactate) sent as per standard of care for all patients.
 5. Hemorrhage control and other diagnostic evaluations performed in all patients per standard of care.
 6. Patients arrive in ICU and have additional blood work (CBC, CMP, possibly ABG, ROTEM viscoelastic test, PT/INR, PTT, venous lactate, possibly fibrinogen) sent per standard of care by the ICU team.
 7. Clinical data on survival and transfusion monitored
- d. Alternative procedures, if any, that are not included in the study but might be advantageous to the subject. N/A

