11. DATA ANALYSIS

Analysis to be performed by median/IQR with nonparametric comparison of medians for central tendency. P value of 0.05 indicates statistical significance. Patients with death on arrival will be excluded from data reporting as they are a different patient population. Intentional sub-analysis will be performed on patients who received less than 6 units PRBC or equivalent in the first 4 hours or 6 units and more PRBC in the first 4 hours (massive transfusion). Also, an intentional sub-analysis will be performed on the patients who were classified as dead on arrival. Separate sub-analyses will be performed on patients with Abbreviated Injury Score (Head) of 3 or greater indicating severe traumatic brain injury.

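### The severe-TBI sub-analysis has no comparison with the other patients and no rule for interpreting it, so a difference in effect could be inferred from subgroup size alone

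*Combined protocol and SAP*

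**What the plan says.** Section 11 (Data analysis) is the whole of the analysis plan. On brain injury it says: "Separate sub-analyses will be performed on patients with Abbreviated Injury Score (Head) of 3 or greater indicating severe traumatic brain injury". The method for the section is "Analysis to be performed by median/IQR with nonparametric comparison of medians for central tendency", and the threshold for the section is "P value of 0.05 indicates statistical significance". The TBI sentence names no endpoint, test or threshold of its own. No analysis of patients with a head score below 3 is described. No interaction test, multiplicity rule or interpretation rule appears anywhere in the document.

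Section 8a gives the reason for interest in TBI. It says that "the inclusion criteria for past studies has been less inclusive than in this trial", and goes on to name the exclusion of severe TBI as the specific example. Section 8f adds that the one earlier randomised trial found lower transfusion volumes once brain-injured patients were left out.

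Section 8f then lists four study questions. None asks whether the effect differs by TBI. The fourth asks whether any benefit is confined to massive transfusion, and for that question section 11 names both strata (below 6 units, and 6 or more).

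**The concern.** Sections 8a and 8f make the TBI result one that readers will want to compare with the rest. Section 11 supplies an overall p-value and a TBI p-value, both naturally read against 0.05, and nothing that measures the difference between the two effects. A non-significant result in a small subgroup is weak evidence about that difference, because it can arise from subgroup size alone. The account in section 8f of the earlier trial already suggests that the effect may not hold in TBI, so a non-significant TBI result beside a significant overall result would look like confirmation. What is at stake is a conclusion about whole blood in brain-injured patients; the primary result is not affected.

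**Working it through.** **Inputs from the documents (section 6).** Effect, alpha and power: "with an expectation of alpha = 0.05 and expected power of 90% to detect a similar 2 unit difference in transfusion volume". Spread: "The standard deviation (estimated from the interquartile range) was approximately 4". Size: "a sample size of 190 should be sufficient; thus our projected sample size of 200 should be more than adequate".

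**Assumptions.** The document gives no TBI share, so 20–50% is used. It gives no allocation ratio (section 8c says only "based on a prespecified calendar-based randomization scheme by week"), so 1:1 is used. Tests are two-sided, the SD is 4 in both strata, and patients are treated as independent.

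**The plan's own figure.** n per arm = 2 × (1.960 + 1.282)² × 4² / 2² ≈ 84.1, so 85 per arm and 170 in total (172 with the t-test). The stated 190 is not reproduced from the stated inputs, although an unstated 10% loss would give 189–192. The gap is on the conservative side: power is 93% at 190 and 94% at 200. It does not affect this point.

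**Power in a stratum.** With m patients split 1:1, SE = 4 × √(4/m) = 8/√m, and power ≈ Φ(2/SE − 1.96). For a 30% share, m = 60, SE = 1.033, 2/SE = 1.936, and power = Φ(−0.024) = 49%. For all 200, SE = 0.566, 2/SE = 3.536, and power = 94%.

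**Chance that the overall result is significant and the TBI result is not.** The overall z-statistic is √f × z(TBI) + √(1 − f) × z(non-TBI), where f is the TBI share. The two results are therefore correlated, and the joint probability was obtained from 400,000 draws. The true effect is 2 units in everyone.

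| TBI share | Power in TBI | Power outside TBI | Overall significant, TBI not | Same, given overall significant |
|---|---|---|---|---|
| 20% | 35% | 89% | 60% | 63% |
| 30% | 49% | 84% | 46% | 49% |
| 40% | 61% | 78% | 34% | 36% |
| 50% | 71% | 71% | 24% | 26% |

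**Dependence on a true effect.** With a uniform 1-unit effect, the overall-significant, TBI-not pattern occurs in 34/30/27/23% of trials. With no effect it occurs in about 4.2/3.9/3.6/3.3%. Discordance between the two strata in either direction is then 2 × 0.05 × 0.95 = 9.5%.

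**Check with a rank test.** Simulating 4,000 trials per share with the Mann–Whitney test and a 2-unit effect gives stratum discordance in either direction of 63/52/46/44%. The normal formula gives 61/51/44/42%. The choice of test is not driving the result.

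**The direct comparison.** The SE of the difference between stratum effects is √(64/m₁ + 64/m₂). For a 30% share this is √(64/60 + 64/140) = 1.234. If the effect is uniform, a test of this difference is significant in about 5% of trials (4.5–5.3% simulated). If the whole 2-unit effect is absent in TBI, its power at 30% is Φ(2/1.234 − 1.96) = 37%. Across the four shares, power is 29/37/41/42%. The difference detectable with 80% power is 2.80 × SE, or 4.0/3.5/3.2/3.2 units.

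**The case against.** The strongest reply is that the plan never sets out to test whether TBI changes the effect. That is right. The question is not among the four in section 8f. Where the plan does ask about effect modification (massive transfusion), it names both strata. Naming one stratum for TBI fits the aim of describing results in patients whom earlier work excluded, and a within-stratum estimate is a legitimate answer to that. A reader might infer that the plan tests the wrong hypothesis; the documents do not support this, because they state no TBI hypothesis.

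A reader might also infer that an effect overall but none in TBI is the likely outcome. That is too strong. Three of the four scenarios in the table fall below one half. All rest on a real, uniform 2-unit effect, and section 13 says that reduced transfusion need has not been shown consistently. The TBI share is assumed. The SD comes from a trial that, by section 8f, excluded significant TBI, so using it inside the TBI stratum is a further assumption.

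Two more points stand. The chance of significance outside TBI but not inside it should not be the headline, because no analysis outside TBI is planned; the overall-versus-TBI figure uses only results that the plan will produce. And the percentages in the table are not strictly comparable with the 5%: they say how often a pattern of p-values occurs, whereas the 5% is how often a formal test would claim a difference. The plan does not prescribe the misleading reading.

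What survives is that the plan does not prevent that reading either, its rationale invites it, and nothing planned measures the contrast.

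**Conclusion.** The point holds as a gap in specification and interpretation. The plan provides a stand-alone TBI result under a section-wide 0.05 rule, with no comparison against patients scoring below 3. If the design effect is true and equal in everyone, the overall result is significant while the TBI result is not in about 60/46/34/24% of trials at TBI shares of 20/30/40/50%. The rate falls with a smaller effect and is low with none.

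These figures rest on N = 200 analysed, 1:1 allocation, a common SD of 4, independent patients and an assumed TBI share. Removing dead-on-arrival patients from the 200, or correlation within allocation weeks, would lower power inside TBI further. The documents do not support saying that the planned method is invalid or that a false TBI conclusion is the expected result.

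**What to change.** In section 11, replace the stand-alone TBI sentence with the following, applied to patients not classified as dead on arrival:

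- Report the treatment effect on 24-hour PRBC equivalents with a 95% CI in both strata, head score 3 or more and below 3.
- Estimate the difference between the two stratum effects (the treatment-by-head-score interaction) with a 95% CI on a named scale. The plan has no regression model to hold an interaction term, so the scale should suit the nonparametric approach. One example is a bootstrap CI for the difference between strata in the between-arm difference in medians, preferably resampling whole weeks because allocation is by week.
- Label the analysis exploratory. State that a within-stratum p-value will not be used to conclude that the effect is present, absent or different in TBI.

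The head score is already collected (section 9), so no new data or patients are needed. The cost is a few sentences and a choice of scale; intervals for medians of whole-unit counts may be coarse, which is a reason to settle the scale in advance.

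The main downside is low power: about 29–42% even if the whole 2-unit effect is absent in TBI. Those figures are for a comparison of means; under the same normal model, a comparison of medians would have less. The confidence intervals must therefore carry the message, and a non-significant interaction must not be read as equal effects.

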12. RISK AND INJURY

This trial is a randomized clinical trial involving a test of two different standard-of-care transfusion strategies. As such, it has been verified by the director of the blood bank that neither of these transfusion strategies involves more than minimal risk. Female patients are excluded at this time to ensure that there is no possibility of inadvertent alloimmunization of Rh-negative childbearing women with Rh-positive blood products. As both the component therapy (O+ or O-) and the O+ whole blood that is administered at LLUMC would be uncrossmatched, there is a risk of transfusion reaction but this risk is not different between groups.

13. BENEFIT(S)

It is possible that patients transfused with LTO+WB may experience improved resolution of coagulopathy. As such it is possible that they may experience either reduced transfusion or even a survival benefit. Thus far, available literature has not demonstrated a survival benefit consistently, nor has it consistently demonstrated reduced need for transfusion. As such, it is felt by the investigators that clinical equipoise still exists between the two randomized treatment arms.

14. COMPENSATION

N/A

15. CONFIDENTIALITY

At the time of data entry into the database, MRN and date of birth will be redacted. A single master list will exist on a LLUMC secure server with the assignment list until the data collection is complete. The RedCap database is endorsed by LLUMC and felt to be secure, and in addition will not contain PHI.

